The HCRV program was started to combat these issues. A designated outreach specialist works with incarcerated VHA-eligible Veterans to establish a post-release plan for linkage to VHA services (2014). This program, with 1-2 outreach specialists per state, has improved the connection between reentry Veterans and the VHA. However, our analyses of homeless program data linked to CDW indicate that 43% of eligible HCRV Veterans **do not** have a VHA outpatient contact in the first 4 months post incarceration. Reducing this number is critical given the elevated rates of chronic health conditions, as well as MH or SUDs in this population (Noonan 2007; Taxman 2010; Maruschak 2012). To address this gap, we will work with the national HCRV office to implement an evidence-based peer support intervention to extend the reach and effectiveness of the HCRV program in linking Veterans to VHA. Peers with incarceration experience are likely to better understand and connect with Veterans on a personal level than the outreach specialist, and thus are more likely to maintain contact and link to VHA during the first months post-release (Blodgett 2013; Chinman, George et al. 2014; Bagnall, South et al. 2015). Peers are gaining popularity in forensic settings (called “forensic peer specialists”) with civilian populations and would likely be beneficial for a Veteran population (Miller and Massaro 2008). The aims of this project are,

1. Conduct contextual analysis to identify VA and community reentry resources, and to describe how reentry Veterans use them.
2. Implement peer-support to link reentry veterans to VHA primary, mental health, and SUD services. We will use external and internal facilitation as the implementation strategy.
3. At the end of this project, we will develop a proposal for a multi-VISN expansion study, which will use a hybrid type III, stepped-wedge design, to demonstrate effectiveness in multiple geographic and contextual settings.

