Phase 1: Contextual Analysis and Preparation for Implementation in Massachusetts. We will conduct contextual analysis (Chambers, Mustard et al. 2013; Chambers, Glasgow et al. 2013; Lyon, Pullmann et al. 2015) through interviews and network mapping (Aim 1). At the end of this phase the findings will be incorporated into the peer-support guidebook. This phase will involve interviewing Veterans (thrice over 6 months) and stakeholders (once). Network mapping is a technique used in business and engineering, and is increasingly being applied in health care. It involves documenting potential paths that individuals and groups follow in the process of accomplishing a task (here, linkage to primary care and other health services)(Lyalin and Williams 2005; Williams, Lyalin et al. 2005; Rico, Yalcin et al. 2014). We use interview questions that seek temporal, spatial, and participatory information. The timing, sequence, and duration of Veterans' contacts with individuals and organizations are mapped in an activity diagram (Lyalin and Williams 2005), which are then combined to comprehensively map the network of reentry-related contacts that Veterans make. These maps may reveal unhelpful contacts, waiting between contacts, and useful but infrequently tapped resources. Population: There are about 200 Veterans, released from Massachusetts prisons each year. Recruitment of Veterans: We will use a method currently in use VHA by a contractor, Policy Research Associates (Delmar, NY), to contact reentry Veterans. During prison visits, the outreach specialists will collect contact information from incarcerated Veterans who indicate willingness to participate in the project after their release. The outreach specialist will provide our team with the contact sheets of those Veterans and their release dates. We will contact these Veterans after their release, enrolling 10 Veterans. Inclusion/Exclusion: Released from an MA state prison, eligible for VHA services, and no history of dementia.

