Additional Design Considerations: The focus of the *Post-Incarceration* project is to develop implementation methods, materials and training, identify appropriate level of internal facilitation, and assess dissemination processes across different states. It is not designed to demonstrate a statistically significant effect of the intervention. With the anticipated sample size of 30 in the peer-support intervention groups and the 30 in the comparison group, the linkage rate, now at 57%, would need to increase by at least 20% to detect the intervention effect with 80% power at the 0.05 significance level. However, our measurement of these outcomes in the current project will allow us to estimate effect sizes and sample sizes for the next phase of this implementation, i.e. a cluster-randomized multi-VISN hybrid implementation-effectiveness study (this next phase will occur after the current project, supported by a separate funding source).

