4. IMPACT

The implementation work described here is highly aligned with our operational partners in the national HCRV program (see letter of support) who recognize many HCRV Veterans are not linking to VHA, and likely are receiving inadequate care from a patchwork of sources. It helps address the known challenge for HCRV of overcoming reentry Veterans’ mistrust of and past negative experiences with large systems – a process that data indicate is best done by a peer. Our project will help answer the question of whether peer-support for Veterans after their incarceration increases VHA linkage rates. Also the project will provide a roadmap (with guidebook, training materials and implementation strategies) so that other states and VISNs can efficiently adapt and implement this peer-support approach in their HCRV programs. The ultimate impact will be an increased rate of linkage to VHA services, substantially beyond the current 57% rate. This linkage will help contribute to improved health and mental health of the thousands of Veterans released from incarceration annually. It has the potential to prevent the cascade of events for many former offenders, when health and mental health deterioration rapidly lead to negative behaviors, re-offending and more incarceration.

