Analysis Plan

Official Title: Veterans Justice Reentry (Post-Incarceration) (QUE 15-284)

Brief Title: Improving Linkage to Health and Other Services for Veterans Leaving Incarceration (PIE)

ClinicalTrials.gov ID: NCT02964897

Unique Protocol ID: QUX 16-012

Study Principal Investigator: D. [name] MS BA

Document date: September 7, 2021

Analysis Plan:

Improving Linkage to Health and Other Services for Veterans Leaving Incarceration (ID QUX 16-012)

We will enroll Veterans on a rolling basis as released from MA correctional facilities. We will use HOMES database to create a historical comparison group comprised of all Veterans released in MA in the two-year period directly preceding the start of the PIE intervention and who accessed VA Health Care for Reentry Veterans (HCRV) services.

Quantitatively, we will use HOMES and CDW to compare intervention and comparison Veterans with respect to their baseline demographic characteristics (age, gender, race, ethnicity, marital status, self-rated health) and our outcomes interest. Also for intervention Veterans we will have self-report diagnoses and utilization from baseline and 6-month follow up (including utilization of non-VA health care sources). We will compare rates of visits for primary care, outpatient MH treatment, outpatient SUD treatment, as well as missed opportunities (e.g. no shows) between intervention and comparison groups using t-tests and chi-square tests. For our secondary measures we will also compare intervention to comparison on ER and hospital use (episodes and # of days) during the 6-month reentry period.

Analysis involves two phases. First, we use descriptive statistics to summarize the volume and intensity of peer activities in support of the Post-Incarceration Engagement (PIE) intervention participants. Secondly, to examine access to and engagement in care outcomes, we compare our measures of linkages to VA health care following release between PIE participants and our historical comparison group. Specifically, we use bivariate tests (Chi-Square/Fisher Exact Tests and t-tests, as appropriate) to assess the relationship between participation in the PIE intervention and linkages with VA health care.

Summary of key variables

- Demographics (age, gender, race, ethnicity, marital status, self-rated health)
- SUD diagnoses
- MH diagnoses
- Criminal offense
- Length of incarceration
- # of arrests
- Housing/homeless experience
- Major comorbidities (out of list of 10-12)

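### With 30 versus 30, a 20-point rise from 57% linkage has about 37% power, not 80%; the rise detectable with 80% power is about 32 points

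*Protocol*

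**What the plan says.** Additional Design Considerations, in section 3 of the Protocol, first disclaims a significance objective: "It is not designed to demonstrate a statistically significant effect of the intervention". The next sentence nevertheless gives a detectable effect. It begins "With the anticipated sample size of 30 in the peer-support intervention groups and the 30 in the comparison group" and says that linkage, currently 57%, "would need to increase by at least 20% to detect the intervention effect with 80% power at the 0.05 significance level". It does not say whether 20% is absolute or relative, or whether the test is one- or two-sided. No other detectable effect appears in either document.

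The 57% is the complement of the 43% in Protocol section 1 who did not "have a VHA outpatient contact in the first 4 months post incarceration".

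The Protocol's Phase 2 analysis compares the groups with t-tests and chi-square tests. The SAP adds Fisher's exact test and uses these tests "to assess the relationship between participation in the PIE intervention and linkages with VA health care". It also replaces the matched comparison group with a historical one, made up of "all Veterans released in MA in the two-year period directly preceding the start of the PIE intervention" who used HCRV services. The SAP gives neither the size of that group nor a power figure.

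**The concern.** Thirty per group is small for comparing two proportions in the middle of the range. The standard error of the difference is about 12 points, so a difference must be close to 24 points before it reaches p = 0.05. A true difference of 20 points therefore cannot have 80% power.

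What is at stake is how the linkage result will be read. Despite the disclaimer, section 4 of the Protocol says "Our project will help answer the question of whether peer-support for Veterans after their incarceration increases VHA linkage rates", and the SAP plans a significance test of linkage. A reader who trusts the sentence would take a non-significant result as fair evidence against a 20-point benefit. With 30 versus 30, such a benefit would be missed about 63% of the time.

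**Working it through.** **Inputs.** From Additional Design Considerations: n = 30 per group, p1 = 0.57, a rise of 20%, 80% power, alpha 0.05. From the Protocol's analysis text and the SAP: unpaired chi-square or Fisher test. Assumed: two-sided testing, with one-sided results also shown.

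**Power for the Protocol's own figure, absolute reading (57% to 77%).** For the chi-square test,

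power = Φ[(|p2 − p1| − z·SE0) / SE1]

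- Pooled rate = (0.57 + 0.77)/2 = 0.67
- SE0 = √(0.67 × 0.33 × 2/30) = 0.1214
- SE1 = √((0.57 × 0.43 + 0.77 × 0.23)/30) = 0.1186
- Two-sided: (0.20 − 1.96 × 0.1214)/0.1186 = −0.320, so power = **37.5%**
- One-sided: (0.20 − 1.645 × 0.1214)/0.1186 = 0.003, so power = **50.1%**

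Full enumeration of both binomials gives 37.3% (chi-square) and 28.1% (Fisher). Unpooled variance gives 39.2% and the arcsine method 38.4%.

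**Relative reading.** 0.57 × 1.2 = 0.684. The same formula gives 14.6% two-sided and 23.1% one-sided. The stated 80% is not reproduced on either reading.

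**Rise detectable with 80% power, 30 versus 30, two-sided.**

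| Method | Detectable rate | Rise (points) |
|---|---|---|
| Chi-square, normal approximation | 88.6% | 31.6 |
| Chi-square, exact enumeration | 88.2% | 31.2 |
| Fisher, exact enumeration | 90.4% | 33.4 |

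One-sided, with the normal approximation, the rise is still 28.5 points.

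**Sample size for a 20-point rise.** n = [1.96 × √(2 × 0.67 × 0.33) + 0.842 × √(0.57 × 0.43 + 0.77 × 0.23)]² / 0.20² = 85.6, so **86 per group**.

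**What observed results would show.** If 17/30 and 23/30 linked (57% versus 77%), chi-square p = 0.10 and Fisher p = 0.17. Against 17/30, the smallest significant count is 25/30 (chi-square p = 0.024, Fisher p = 0.047).

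**The SAP's historical group.** Its size is not stated, so a range is assumed. The upper value of 400 comes from the Protocol's Phase 1 statement that "There are about 200 Veterans, released from Massachusetts prisons each year", taken over two years. It ignores the restriction to HCRV users, and the Protocol figure covers prisons only, so 400 is an assumption and not a firm ceiling. The lower value of 100 is illustrative. Two-sided chi-square, 30 intervention Veterans, 57% versus 77%:

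| Comparison group | Power for +20 points | Rise detectable with 80% power (points) |
|---|---|---|
| 100 | 51% | 26.7 |
| 200 | 56% | 25.3 |
| 400 | 58% | 24.6 |
| Unlimited | 62% | 23.8 |

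A true 20-point rise would thus be missed about 42% to 49% of the time with 100 to 400 comparators.

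**Precision.** The 95% confidence interval half-width is 1.96 × √(0.57 × 0.43/n_c + 0.77 × 0.23/30), where n_c is the comparison-group size. This gives 23 points for n_c = 30, 18 for 100 and 16 for 400.

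**The case against.** The strongest reply is that the sentence is a caveat under an explicit disclaimer. The 30 intervention Veterans match two peers with caseloads of 15, not a power calculation; no decision rule depends on a significant linkage result; and the next study is to be sized from the effects measured here. All of this stands, and it keeps the point from being more serious. It does not make the number correct, and the error makes the caveat far too mild.

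Other possible rescues:

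- **Matching.** The Protocol's 30 comparators were to be matched, but the planned tests are unpaired. Even a matched-pairs test at its theoretical best (20% of pairs discordant, all in one direction) reaches only about 71% two-sided. A one-sided test at that extreme would pass 80% (about 82%), but neither document plans one.
- **A different variance for the historical comparison.** The 62% limit belongs to the two-sided chi-square test. An unpooled test gives 70% with 400 comparators and 74% with an unlimited group. An unpooled one-sided test with an unlimited group would reach about 83%. The SAP plans chi-square or Fisher, and every two-sided version stays below 80%.
- **The design has moved on.** The SAP no longer plans 30 versus 30, so correcting that sentence alone would leave the current analysis undescribed. This is fair, and it is why the fix covers the SAP as well.

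**Conclusion.** The statement is wrong. With 30 versus 30 and two-sided 0.05, power for a 20-point rise from 57% is about 37% (28% by Fisher), and the rise detectable with 80% power is about 32 points (about 33 by Fisher). The relative reading is worse, at about 15% power. No standard unpaired two-group method reproduces the claim, one- or two-sided.

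The 30-versus-30 result needs no assumption beyond two-sided testing. The historical-group figures depend on an assumed size of 100 to 400, but the conclusion does not: under the planned two-sided chi-square test, no comparison-group size lifts power for 20 points above about 62%.

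This should be fixed. It affects how the linkage result is interpreted, not enrolment or conduct.

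**What to change.** 1. In the Protocol, keep the disclaimer and replace the power sentence with: *With 30 versus 30 and a two-sided 0.05 test, 80% power requires linkage to rise from 57% to about 89% (about 32 percentage points); power for a 20-point rise is about 37%.*
2. In the SAP, state the actual number of historical comparators and the rise detectable with 80% power at that number.
3. Report the linkage difference with its 95% confidence interval. This also serves the stated aim of estimating effect sizes for the next study better than a p-value alone.

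A secondary, optional clarification is to state the window over which linkage is counted. The 57% is a 4-month rate, and neither document fixes a window for linkage.

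The cost is wording, one count from HOMES and one added interval. No extra Veterans are needed and the planned tests stay as they are. The stated detectable effect becomes less favourable.

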4. IMPACT

The implementation work described here is highly aligned with our operational partners in the national HCRV program (see letter of support) who recognize many HCRV Veterans are not linking to VHA, and likely are receiving inadequate care from a patchwork of sources. It helps address the known challenge for HCRV of overcoming reentry Veterans’ mistrust of and past negative experiences with large systems – a process that data indicate is best done by a peer. Our project will help answer the question of whether peer-support for Veterans after their incarceration increases VHA linkage rates. Also the project will provide a roadmap (with guidebook, training materials and implementation strategies) so that other states and VISNs can efficiently adapt and implement this peer-support approach in their HCRV programs. The ultimate impact will be an increased rate of linkage to VHA services, substantially beyond the current 57% rate. This linkage will help contribute to improved health and mental health of the thousands of Veterans released from incarceration annually. It has the potential to prevent the cascade of events for many former offenders, when health and mental health deterioration rapidly lead to negative behaviors, re-offending and more incarceration.

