of the first Veteran-peer encounters will involve accompanying the Veteran to his first VHA health care appointment and orienting him to check-in, appointment making, laboratory, and pharmacy. Other encounters may include reviewing health-related priorities and goal setting, assistance with health tasks (e.g. refilling prescriptions), and brief motivational interviewing related to health goals. Training of peers will be conducted by Drs. [name], [name], [name] and [name], over a 4-day period, at Bedford VAMC. Following training, the HCRV team (VISN coordinator(s), outreach specialists, and peers) will participate on twice monthly conference calls, led by the trainers and the external facilitators ([name] and [name]), to discuss issues that arise in the use of peer support.

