Implementation Frameworks and Strategy: Guided by our QUERI's selection of Consolidated Framework for Implementation Research (CFIR), we will ensure that our intervention is appropriate for the contexts in different states. Context, in CFIR, is delineated by the domains of Outer Setting (e.g. external policies, patient needs and resources) and Inner Setting (e.g. structure of the organization, culture). As with the other BridgeQUERI projects, we have selected facilitation as our implementation strategy. In addition our peer-support intervention is enhanced by the Behavioral Model for Vulnerable Populations (BMVP), (see description of BridgeQUERI Implementation Core), namely **Predisposing** characteristics (demographics, social structure, health beliefs), **Enabling** characteristics (personal/family, community, insurance, competing needs, ability to negotiate bureaucracy), and health-related **Need** based factors(perceived and evaluated health conditions). We propose both **external** and **internal** facilitation, because we are working in a complex setting with a highly complex population (Stetler, Legro et al. 2006; Jones, Auton et al. 2008; Kirchner, Kearney et al. 2014). To our knowledge there has been no evaluation of facilitation as an implementation strategy for state-level implementation of a VA program. Thus we have an excellent opportunity to contribute to the VA knowledge base on using facilitation as an implementation strategy. Additionally, we will vary the organizational level of internal facilitation. The internal facilitator will be one of the Outreach Specialists ([name], LCSW). Facilitation will include use of a manualized peer-support training (using a peer-support guidebook from Aim 1), and ongoing problem solving and technical assistance provided to VISN HCRV leadership, outreach specialists, and peers over the course of the project. Our implementation strategy was developed with our operational partners at HCRV program. They have great interest in HCRV program differences from state to state, realizing that states vary considerably in the resources available for reentry programs, and the supportiveness of the culture in relation to ex-offenders.

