Project Plan Overview: We propose to implement the Post Incarceration Engagement intervention in Massachusetts using a facilitation implementation strategy. We conduct formative and summative analyses, including assessment of fidelity, and a matched comparison group to evaluate the intervention's Veteran outcomes of linkage and engagement in VHA health care (using health care utilization measures). The project proceeds in 3 phases (see Figure 1). First, in preparation for implementation of peer-support intervention in the first state, we will conduct a contextual analysis in MA of the resources available in VHA and in community organizations to meet the needs of Veterans released from incarceration (Aim 1), development of peer-support guidebook (based on findings of the contextual analysis) and hiring of 2 peers. Next the intervention will be implemented in MA (Aim 2). It will last 6 months with a total of 30 Veterans receiving the peer support. We will identify a matched sample of comparison reentry Veterans. Qualitative formative and summative interviews will be conducted with a sample of stakeholders and Veterans to assess fidelity of the intervention. A review of peer worksheets documenting contacts with Veterans will also help evaluate fidelity evaluation. Utilization of VHA primary care, mental health care, and SUD care will be evaluated through chart reviews, and self-report (self-report for intervention Veterans only). Finally we will develop a proposal for the spread of this intervention through the use of a cluster-randomized multi-VISN hybrid implementation-effectiveness study (Aim 3).

Design and Methods: Key Outcomes: Our Veteran level outcomes include # of primary care visits, MH visits, and SUD visits (where diagnosis indicates appropriateness); and missed opportunity rates (no-shows and cancellations) for primary care, MH, and SUD visits. Secondary outcomes include # of emergency room (ER) visits, hospitalizations, and hospital days – these are also being assessed in the BridgeQUERI MISSION project, providing cross-project comparisons. Our main implementation outcome will be fidelity of the intervention as implemented, in comparison to core elements as contained in the peer-support guidebook. We use a practical approach based on the NIH's Behavioral Change Consortium fidelity framework for psychosocial Treatments (Bellg, Borrelli et al. 2004). Our two primary fidelity measures are number of peer

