Analysis: During implementation we will collect formative evaluation data about the intervention through interviews (5 stakeholders and 5 Veterans). We will assess elements of the implementation by learning what meanings the participants (stakeholder, peers, Veterans) assign to the intervention and the processes that the intervention is designed to affect (Orlikowski and Baroudi 1991). We will also conduct summative evaluation, including qualitative interviews (5 Veterans and 5 stakeholders) to evaluate, for example, whether peers were *Enabling* linkage to and engagement in health care, and whether this helped address Veteran’s health care *Need*. With stakeholders we will explore the effectiveness of external and internal facilitation, and identify facilitators and barriers to implementation. Quantitatively, we will use HOMES and CDW to compare intervention and comparison Veterans. Also for intervention Veterans we will have self-report diagnoses and utilization from baseline and 6-month follow up (including utilization of non-VA health care sources). We will compare rates of visits for primary care, MH, and SUD between intervention and comparison groups using t-tests and chi-square tests. For our secondary measures we will compare intervention to comparison Veterans on ER and hospital use (episodes and # of days) during the 6 month reentry period.

Key Covariates. We will use CDW and HOMES data to evaluate whether there are substantial differences between the intervention and comparison Veterans at baseline. This approach accounts for the possibility that observed differences in our outcomes, such as linkage rates, may be partially explained by factors such as duration of sentence, severity of crime, number of incarcerations, ever used VHA services, length of time since last used VHA services, and socio-demographics such as age and race.

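### Under the SAP's historical comparator, the linkage difference estimates the facilitated PIE package plus any change over time, not peer support alone.

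*Protocol*

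**What the plan says.** **The question.** Protocol section 4 (Impact): "Our project will help answer the question of whether peer-support for Veterans after their incarceration increases VHA linkage rates".

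**How PIE is delivered.** Protocol section 3, Project Plan Overview: "We propose to implement the Post Incarceration Engagement intervention in Massachusetts using a facilitation implementation strategy". Under Implementation Frameworks and Strategy, facilitation has two parts. One is tied to the peers: "Facilitation will include use of a manualized peer-support training". The other reaches further: "ongoing problem solving and technical assistance provided to VISN HCRV leadership, outreach specialists, and peers over the course of the project". One outreach specialist is the internal facilitator. Under Peer-Support Interventions: "Following training, the HCRV team (VISN coordinator(s), outreach specialists, and peers) will participate on twice monthly conference calls". The stated topic of those calls is issues arising in the use of peer support.

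**The comparator, in two versions.** Protocol section 3, Phase 2, draws a matched group from HOMES among Massachusetts Veterans released over the same months as the intervention group. The SAP uses a "historical comparison group comprised of all Veterans released in MA in the two-year period directly preceding the start of the PIE intervention", restricted to those who accessed HCRV services. It plans bivariate tests only and names no adjustment for calendar time.

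**How facilitation is assessed.** Protocol section 3, Phase 2 Analysis: "With stakeholders we will explore the effectiveness of external and internal facilitation". This is interview work.

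**Use of the result.** Protocol section 3, Additional Design Considerations, says the study is not designed to show a statistically significant effect, but that its outcomes will supply effect sizes and sample sizes for the next, cluster-randomized study.

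**The concern.** The Protocol treats peer support as the intervention and facilitation as the strategy for implementing it. With same-period comparators in the same state, help given to HCRV staff would be largely shared by both groups, and so would anything else that changed over time. Moving the comparators to the two preceding years removes that protection. Linkage could then be higher among PIE participants because of the peers, because staff who serve every HCRV Veteran worked differently, or because linkage in Massachusetts was changing anyway. Section 1 of the Protocol puts the programme at one or two outreach specialists per state, so a change in their practice could reach most HCRV Veterans, with or without a peer.

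The stake is interpretation. A package-plus-period difference could be reported as a peer-support effect and then used under that label to plan the expansion study.

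**Working it through.** **1. What differs between the groups**

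| | PIE participants | Protocol comparators (same period, matched) | SAP comparators (preceding two years) |
|---|---|---|---|
| Peer support | yes | no | no |
| Outreach specialists and leadership facilitated | yes | largely yes, same state team | no, or only partly |
| Calendar period | PIE enrolment | PIE enrolment | earlier |

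The entry for the SAP comparators is qualified because the Protocol says facilitation runs through the whole project and the timeline figure is not shown. Some earlier project activity may overlap the two historical years.

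For the SAP contrast:

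expected difference = peer effect + effect of facilitation on staff's own work + period change (+ any difference in case mix).

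A two-group test estimates only this sum. More historical Veterans make the sum more precise but do not split it.

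**2. The plan's own figure**

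Additional Design Considerations gives 80% power at 0.05 for 30 v 30 and a rise of at least 20% from 57%. Reading this as 57% to 77%, two-sided, pooled variance:

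- se0 = √(2 × 0.67 × 0.33 / 30) = 0.1214
- se1 = √((0.57 × 0.43 + 0.77 × 0.23) / 30) = 0.1186
- power = Φ((0.20 − 1.96 × 0.1214) / 0.1186) = 37.5%

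Read as a relative rise to 68.4%, power is 14.6%. The 80% does not reproduce. That is a separate problem and neither supports nor refutes this point.

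**3. What an unmeasured shift would do (illustration only)**

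The documents give no size, or even direction, for a facilitation or period effect. Assume the peer effect is zero and the later period is higher by d. With N comparators at 57% and 30 PIE Veterans at 57% + d, using pooled se0 and unpooled se1 as above:

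P(p < 0.05) = Φ((d − 1.96·se0)/se1) + Φ((−d − 1.96·se0)/se1).

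| d (assumed) | 30 v 30 | 30 v 400 |
|---|---|---|
| 5 points | 6.8% | 7.9% |
| 10 points | 12.4% | 17.6% |
| 15 points | 22.6% | 35.0% |
| 20 points | 37.5% | 58.4% |

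The nominal rate is 5%. The 400 is the most that two years at about 200 Massachusetts releases a year (section 3, Phase 1) could supply; the share using HCRV is not given. The bias is d at any sample size.

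**4. What a same-period, no-peer group could show**

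Inputs: about 200 releases a year, 30 PIE Veterans, linkage of 57% in both groups. The length of enrolment is not stated. The 80% VA-eligible share is the national figure in section 1.

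95% half-width = 1.96 × √(0.57 × 0.43 × (1/n₁ + 1/n₂)).

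| Assumption | Same-period n | PIE v same-period | Historical v same-period |
|---|---|---|---|
| One year, all use HCRV | 200 − 30 = 170 | 30 v 170: 19.2 points | 400 v 170: 8.9 points |
| One year, 80% | 160 − 30 = 130 | 30 v 130: 19.7 points | 320 v 130: 10.1 points |
| Six months, all use HCRV | 100 − 30 = 70 | 30 v 70: 21.2 points | 400 v 70: 12.6 points |
| Six months, 80% | 80 − 30 = 50 | 30 v 50: 22.4 points | 320 v 50: 14.8 points |

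However many comparators there are, the 30 PIE Veterans alone hold the PIE contrast above 1.96 × √(0.2451/30) = 17.7 points. The same-period linkage rate taken by itself has a half-width of 7.4 points at n = 170, but that is not the precision of either contrast.

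**The case against.** **The Protocol already has the right comparator.** This stands as a fact. A reader of the SAP alone might infer that no planned group had facilitation without a peer. The Protocol's Phase 2 group contradicts that. But the SAP does not use that group and gives no reason, so the conflict is part of the point.

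**Much of facilitation is how peer support is delivered.** This also stands for the peer training and for calls about using peers. Only help that changes outreach specialists' own work is a separate cause. The Protocol describes no such change, and section 2 says HCRV already does reentry planning well, the gap being staff time after release. So the facilitation share may be small. Period change remains, and the package label is accurate either way.

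**The Protocol makes no firm claim.** It speaks of helping to answer the question and disclaims a design for significance, and the SAP speaks of participation in PIE. A reader might infer that the plan credits any difference to peers outright; the text does not go that far. But disclaiming significance deals with power, not bias, and the effect size is still to be carried forward.

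**The expansion study may want the package effect.** If that study again pairs peers with facilitation, the package effect is the relevant planning figure. It should then be labelled as such, and period change is still not part of it.

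**Scope and timing.** One might infer that facilitation covered HCRV as a whole and began on the day peer support did. The documents describe facilitation of VISN leadership, outreach specialists and peers, and do not state a common start.

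**Facilitation's effectiveness.** The sentence on exploring it with stakeholders is plainly qualitative and needs no change.

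**Conclusion.** The point holds under the SAP's comparator. The planned difference in linkage estimates the facilitated PIE package plus any period change, while Protocol section 4 poses a question about peer support. It would hold to a much smaller degree under the Protocol's same-period group, where staff facilitation and calendar time are largely shared.

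The size of the misattribution is unknown. It is tempting to say that facilitation could account for a quarter to a half of a 20-point gain, but that only restates an assumed shift of 5 to 10 points (5/20 and 10/20). The documents supply no such figure, and the Protocol's 20% may not mean points.

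Nor would a same-period group settle the matter. At about 19 points for PIE v same-period and about 9 for historical v same-period under the most favourable one-year assumptions, it could not resolve a 5-point facilitation effect and could barely resolve a 10-point one. A shorter enrolment or lower HCRV use widens both. Its value is to show whether linkage moved in Veterans without a peer. This is an inexpensive improvement to interpretation.

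**What to change.** 1. Reconcile the Phase 2 comparator in Protocol section 3 with the SAP's historical group. State in the SAP and in Protocol section 4 that the historical contrast estimates the facilitated PIE package plus any change over time.
2. Add to the SAP a HOMES/CDW extract of Massachusetts HCRV Veterans released during PIE enrolment who received no peer, with the variables already listed. Report their linkage and visit rates beside those of the PIE and historical groups. Historical against same-period shows change from staff facilitation and time together; PIE against same-period is the contrast nearest to the peer component.
3. Label the added column descriptive. Non-enrolled Veterans differ from those who volunteered, and precision is low. Give intervals for the differences as well as for each rate.

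Cost: SAP and Protocol wording plus one extract from sources the study already uses, with no new enrolment. The downsides are a narrower claim and a third column that needs a selection caveat.
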